Characteristics of an Adverse or Serious Adverse Event	22
Relationship to Study Intervention	22
Expectedness	22
Severity	22
Reporting Procedures	22
Protocol Deviations and Other Unanticipated Problem Reporting	23
Privacy	23
12. Data management	24
13. Data & Safety Monitoring Plan	25
Plans for Assurance of Compliance regarding Adverse Event Reporting.	25
Plans for Assuring Data Accuracy and Protocol Compliance.	25
Data Safety Monitoring Board (DSMB).	25
Quality Assurance and Confidentiality	26
Confidentiality	26
14. Privacy, Data Storage & Confidentiality – see Research Data Security Plan.	26
15. IRB of Record	26
Appendix 1: Schedule of Events	30
Appendix 2: Study Workflow	310
Appendix 3: Randomization Arms	31

Abbreviations and Definitions

- Activities of Daily Living (ADLs)
 - An assessment designed to assess one's ability to complete basic self-care skills.
- Adverse Event (AE)
 - Any untoward medical occurrence associated with or observed in the context of a study procedure. For this study and patient population, an AE will be considered any suicidal ideation. No other events will be considered AEs as this patient population is ill and it is expected that other untoward medical occurrences will occur.
- Clinical Trial Management System (CTMS)
 - For this study, a CTMS known as OnCore will be utilized to manage the study's administrative responsibilities and subject level documentation.
- Duke Regional Hospital (DRH)
 - Study site in which eligible patients will be enrolled.
- Duke University Hospital (DUH)
 - Study site in which eligible patients will be enrolled.
- Oregon Health & Science University (OHSU)
 - Study site in which eligible patients will be enrolled.
- University of Colorado-Denver (COL)
 - Study site in which eligible patients will be enrolled.
- University of Washington-Seattle (UW)
 - Study site in which eligible patients will be enrolled.
- Electronic Data Capture (EDC)
 - For this study, the EDC will be supported and secured by Duke University via REDCap in which relevant study data, such as screening, enrollment, and clinical variables both from research participants' medical records and app will be documented.
- Electronic Health Record (EHR)
 - Used interchangeably with EMR; the EHR is the patient-specific medical record located in the secure MaestroCare (aka: EPIC) or other electronic medical record platform.
- Electronic Medical Record (EMR)

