 - Defined as an adverse event that is both serious and expected in nature; the event may have a reasonable possibility that it is related to a study. SAEs for this study are defined as a suicide attempt, a hospitalization, or death.
- Suicide Ideation (SI)
 - The idea of committing self-harm and/or the intent to act on the idea of committing self-harm.
- Unanticipated Problem (UP)
 - Any other event, not meeting the definition of PD, UP, AE or SAE that, in the opinion of the principal investigator, merits documentation as it occurred outside the expected design of the study and/or study procedures. These events, like PDs, UPs, AEs, or SAEs, may be reported to the IRB and/or the study sponsor, as applicable.

Clinical Protocol Synopsis

1. Title

Optimizing a self-directed mobile mindfulness intervention for improving cardiorespiratory failure survivors' psychological distress (a.k.a., 'LIFT2')

[figure not shown]
2. Background & Rationale

As survival has improved for the 2 million people with cardiorespiratory failure managed annually in the US intensive care units (ICUs), it has become apparent that these patients suffer from severe and persistent post-discharge symptoms of psychological distress including depression, anxiety, and post-traumatic stress disorder (PTSD). However, few targeted interventions exist that are relevant to patients' experiences and that accommodate their many physical, and social barriers to personalized care. To fill this gap, we developed an innovative app-based mobile mindfulness training program that promotes automated care delivery and self-management of symptom-related distress.

Previously, a pilot randomized clinical trial (RCT) called LIFT (R34 AT00819) in which this project is built on, compared mobile mindfulness to both a standard telephone mindfulness program and an ICU education control among survivors of cardiorespiratory failure. LIFT demonstrated that mobile mindfulness was feasibly delivered, acceptable, usable, and had a greater clinical impact on psychological distress than either comparator. This trial also highlighted opportunities to improve the intervention's impact related to its targeted population, content delivery, and system technology.

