Plans to prevent coercion of patients and to ensure voluntary participation

We will strive to create an environment free of any coercive practices for patients. We will stress that study involvement is voluntary and that choosing to participate or not participate will not affect their care in anyway. In addition, we will utilize the standardized 2-minute informational video, which has been used successfully in past trials describe treatment groups and ensure a similar approach across sites.

Specific longitudinal participant oversight plans for severe psychological distress (including suicidal ideation)

Given the difficult situations faced by patients, we recognize that there is a slight risk that some participants may become distressed completing questionnaires or viewing study materials, as mentioned above.

We will take the following measures to prevent any negative reactions as well as effectively manage any serious distress that occurs:

- (1) All of the in-person and telephone-based data collection sessions will be conducted by study team members who are sensitive to the issues that arise.
- (2) Study team members will emphasize to participants that any interviews or other study interactions are participant-controlled. Thus, participants will be instructed that they are in control over what they share and generally how long they discuss any topic that is addressed.
- (3) Participants will be told that they can discontinue an interview or telephone session at any time and that they are free to reschedule an interview or treatment session at any time within the week.
- (4) Overall, we are very sensitive to the common and pervasive nature of psychological distress among ICU survivors and are experienced in discussing these issues with them. There is also a potential risk for identifying underlying mental health issues through the mMT sessions, telephone calls, and survey responses. For issues such as passive suicidal ideation or symptoms of depression, anxiety, or PTSD, an informational sheet will be provided with contact numbers for additional mental health services. Additionally, at the beginning of the program, all subjects will be informed that the training program may uncover unresolved and distressing thoughts or feelings; and a list of resources will be provided at that time.

Suicidality Response Plan

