First, delegated study team members may have in-person or telephone interactions that concern them. Second, the study app system will automatically detect any endorsement of active suicidal intent in a 2-step process that is contingent on the PHQ-9's item # 9 which evaluates suicidal thoughts and the C-SSRS item #4 which evaluates intent by asking "have you had these thoughts and had some intention of acting on them? (as shown below:

PHQ-9 item 9 response	Suicidal intent item response	Action by app system	Action by team
0	n/a	n/a	n/a
1, 2, or 3 (i.e., ≠ 0)	NO	n/a	n/a
1, 2, or 3 (i.e., ≠ 0)	YES	Alert to study manager, therapist, and PIs	Immediately contact participant

Should a patient indicate to a study team member or via the app, thoughts of suicidality or ideation of suicidality, the Suicidality Response Plan could be activated.

If the participant is deemed to be at high risk based on direct interaction plus the C-SSRS item response, the delegated study team member will administer the C-SSRS to assess the participant to determine if they endorse active suicidal ideation. The trained staff will also determine if the participant is currently being treated by a mental health professional.

If the patient is deemed not to be actively suicidal, they will be given a list of local mental health resources as follows:

- Duke University: Call Emergency Psychiatry at [contact] or [contact], available 24 hours a day, 7 days a week.
- Oregon Health & Sciences University: National Suicide Prevention Lifeline - [name]
- University of Colorado: Call Psychiatric Emergency services at [contact], a 24-hour resource line

All sites, may use, as a backup: The National Suicide Prevention Lifeline - [name] is a free, 24-hour hotline available to anyone in suicidal crisis or emotional distress.

If the participant is considered actively *suicidal* then at least one of the following plans will be followed depending on the location of the participant for each of the following situations:

- Situation 1
 - If the participant is with one of the study personnel, the study personnel will notify the site PI one of the other PIs immediately.
 - The study personnel will either physically walk the subject to the emergency department, or call a Psychiatric Emergency services number relevant to the site as described above.
- Situation 2
 - If the participant is on the telephone:

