3. Severe: significant symptoms requiring invasive intervention; subject seeks medical attention, needs major assistance with ADL

Reporting Procedures

Adverse and Serious Adverse Events

For symptoms that are either great in total burden (i.e., total score is high), a delegated study team member (e.g., therapist) will call the participant to check in. For specific symptoms such as the suicidal ideation, a delegated study team member will also call the participant and assess the severity of the situation, triaging them as appropriate to psychiatric support.

For other matters, the study team will maintain frequent telephone contact with most participants, and can refer those with concerning symptoms.

All deaths will be reported to NIH Program Officer and to the DSMB Chair within 72 hours of study's knowledge of death. For each patient who dies, a brief report containing the following variables will be provided:

- Age
- Principal diagnosis
- Number of comorbidities
- Admission APACHE II score

- Days since enrollment
- Brief description of circumstances surrounding death including expected or unexpected.

Serious (fatal or life-threatening) SAEs that are unanticipated and that are related to the intervention will be reported to the NHLBI Program Officer and to the DSMB Chair within 7 days of study staff's knowledge of the SAE.

The summary of all other SAEs will be reported to NIH Program Officer and to the DSMB quarterly, unless otherwise requested by the DSMB.

Protocol Deviations and Other Unanticipated Problem Reporting

Incidents or events that meet the reporting criteria, as outlined by the Duke IRB, will be reported to the Duke IRB as needed.

The following will be included, at a minimum:

- A detailed description of the event, incident, experience, or outcome;
- A description of any changes to the protocol or other corrective actions that have been taken or are proposed in response to the unanticipated problem.

Reporting for Multi-Center Trials

The study site must immediately report to the coordinating center and study manager any serious adverse event, whether or not considered study related, including those listed in the protocol and must include an assessment of whether there is a reasonable possibility that the study caused the event within 48 hours of PI awareness of the event.

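### For suicidal thoughts without stated intent, the response table asks for no action while Reporting Procedures promises a call, and no mandatory rule brings the PHQ-9 item 9 answer to staff or into the AE record

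*Protocol*

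**What the plan says.** The case of item 9 scored 1 to 3 with a negative answer on intent is touched in several places in the Protocol.

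- **Section 12, Suicidality Response Plan.** The automated rule is aimed at intent: "the study app system will automatically detect any endorsement of active suicidal intent in a 2-step process". In the table, only the intent YES row carries an action: for the app it is "Alert to study manager, therapist, and PIs", and the team makes contact at once. The intent NO row is n/a in both action columns. The text after the table says that when suicidal thoughts are disclosed to staff or through the app, "the Suicidality Response Plan could be activated".
- **Section 12, oversight plans for severe psychological distress, item 4.** "For issues such as passive suicidal ideation or symptoms of depression, anxiety, or PTSD, an informational sheet will be provided".
- **Section 12, Reporting Procedures.** "For specific symptoms such as the suicidal ideation, a delegated study team member will also call the participant", with an assessment of severity and triage. A separate call is planned in the sentence that begins "For symptoms that are either great in total burden (i.e., total score is high"; no cut-off is given.
- **Abbreviations and Definitions.** Suicide ideation is "The idea of committing self-harm and/or the intent to act on the idea of committing self-harm". On adverse events: "an AE will be considered any suicidal ideation". The AE paragraph of section 12 repeats this and adds only distress tied to the questionnaires or the coping skills practice.
- **Section 12, Period and Frequency for Event Assessment, and Appendix 1.** Staff ask about AEs at each study visit, by request or by record review. Appendix 1 marks AE/SAE assessment at Day 0, T1, T2 and T3.
- **Section 14, Data Safety Monitoring Board.** AE reports are one of the two primary safety measures.

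**The concern.** A site that works from the table does nothing for this participant. A site that works from Reporting Procedures telephones. Both are following the Protocol.

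Two things are at stake. The first is the participant's safety: the call in Reporting Procedures is where someone would judge how serious the thoughts are, and the table would let it be missed. The second is safety reporting. Suicidal ideation is the main event that this trial counts as an AE. If an item 9 answer reaches the AE log at some sites and not at others, the AE reports that the DSMB reviews will partly reflect site practice.

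**Working it through.** No calculation settles this. The check follows one participant through every contact and AE rule in the Protocol. The case is item 9 of 1, 2 or 3, intent denied, total score not high, and total not above the T1 value.

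| Rule | Where | Result for this participant |
|---|---|---|
| Automatic alert | Section 12, Suicidality Response Plan table | Not sent; needs intent YES |
| Team action | Same table | n/a |
| Response plan | Same section, text after the table | Optional; no criterion given |
| Information sheet | Section 12, oversight plans, item 4 | Provided for passive ideation; no call attached |
| Call for high total | Section 12, Reporting Procedures | Not met |
| Contact at T2 or T3 | Section 7, Study Visits | Not met; needs an alert or a score above T1 |
| App mechanism for rising distress | Section 3, Aim 2 | Distress has not risen; even then it only may alert |
| Weekly check-in | Appendix 1, note d | A safety check, but its items are not listed |
| Call for suicidal ideation | Section 12, Reporting Procedures | Promised; no rule tells staff of the answer |
| AE inquiry at visits | Section 12 and Appendix 1 | Scheduled; record review alone is allowed |

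**Is this participant covered by the promised call?** Yes, as worded. The definition of ideation joins the idea and the intent with and/or, so the idea alone is enough. The call is not limited to alerted cases.

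**Is the event an AE?** Yes, under both the definitions section and the AE paragraph of section 12.

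**Would it be recorded?** It may be. A verbal, written or telephone inquiry could bring it out. Review of the hospital record need not, because the answer was given in the app. No rule has staff read the item 9 answer for AE entry.

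**What about T1?** The rule based on a rise since T1 cannot apply at T1 itself. A patient can also endorse item 9 and still fall below the entry cut-off of 5. The PHQ-9 total is the sum of its items, so item 9 of 1 with 0 to 3 points elsewhere gives a total of 1 to 4, and item 9 of 3 with 1 point elsewhere gives 4. Section 7 has the app tell such a patient that participation is over, so there is no T2 or T3. The patient has already consented, and section 12 has AEs recorded from consent.

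**How many?** The documents give no rate of item 9 endorsement without intent. The figure of under 5% in the Suicidality Response Plan counts calls by the PI in past studies, which is a different quantity.

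**The case against.** The best defence is that the Protocol describes a graded plan: resources for passive ideation, alert and contact for intent. The table follows a sentence about active intent, the information sheet fits its intent NO row, and all participants receive a resource list at the start. On that reading only one general sentence in Reporting Procedures is out of step. This largely stands. The sheet and the table are compatible, and a reader who infers three irreconcilable instructions goes too far. The conflict is between that plan and the promised call, and it remains because the call is not restricted to intent.

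A reader might also infer that nothing prompts an AE record. The documents do not support that, since AE inquiry is scheduled at each visit and can be verbal, written or by telephone. What is missing is a rule tying the item 9 answer to the AE log.

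Nor is the participant out of reach. The response plan may be activated for ideation given through the app, weekly check-ins look at safety, and Reporting Procedures expects frequent telephone contact with most participants. None of these is a mandatory response to the answer.

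Finally, section 14 leaves AE definitions and the procedure for reporting and responding to AEs to the DSMB charter, which is not among the documents. It may settle part of this. The Protocol would still contradict itself.

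**Conclusion.** The point holds in a limited form and should be corrected. For item 9 of 1 to 3 without intent, the response table and Reporting Procedures disagree on whether staff call. When the total is neither high nor above its T1 value, no mandatory rule brings the answer to anyone. AE capture then depends on the visit inquiry, which may be record review alone.

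This rests on reading ideation as the Protocol defines it and on the charter not already supplying the rule. The number of participants affected is unknown. Counting planned PHQ-9 forms would not measure it, because a form matters only if item 9 is endorsed and intent is denied. It would also be too strong to say that every such answer must lead to a call within a fixed time: the threshold and timing are clinical decisions for the investigators.

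**What to change.** Change the intent NO row of the Suicidality Response Plan table to three actions: a non-urgent flag to the study manager and therapist, the information sheet from the oversight section, and review of the item 9 answer for entry as an AE. Apply it at every PHQ-9, including T1 forms that score below 5.

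Then make the table and Reporting Procedures agree on the call. As Reporting Procedures now stands, that means a brief safety-only call by existing staff, with timing set by the investigators and each call logged by randomised condition. Limiting the promised call to alerted cases would also remove the contradiction, but it gives up a contact that the Protocol now promises. The flag and the AE review are needed either way.

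The cost is one table row, one alert rule, matching text and some short calls. The downside is added human contact where therapist versus app is the randomised contrast. Groups 2, 3, 4, 6, 7 and 8 have app help, app introduction or both: 6 × 30 = 180 of 240 participants, of whom 2 × 30 = 60 (groups 4 and 8) have both. Only those with a flagged answer would be called, so 180 is a ceiling and not an estimate. A script without mindfulness or app content limits the effect, and the log lets it be examined. Safety contact for intent, a high total or a risen score is already written without regard to condition.

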The weekly check-ins and surveys completed at baseline, hospital discharge (T1), 1 (T2) and 3 (T3) months will be used to assess changes in distress and anxiety levels. Each survey includes a combination of the following assessments: PHQ-9, PHQ-10, GAD-7, PTSS, MAAS, as well as medical services, sociodemographic, financial and social support, quality of life questions, and ADL/IADL assessments.

Adherence to the mMT plan will be assessed throughout the patient's participation. Depending on randomization group, patients may receive therapist intervention introducing them to the concept of mindfulness and then receive frequent follow-ups from the study therapist to provide training, education and support. The mMT app provides a built-in safety mechanism that detects increased levels of distress and may alert the study team (i.e., site PI, study manager, and study therapist) of the increased distress levels. In doing so, a delegated member of the study team will follow-up with the patient and assess their safety and overall well-being, as outlined in section 12.

Aim 3: Explore barriers and facilitators to mMT implementation and dissemination.

Using qualitative analysis of semi-structured interviews in up to 40 participants enrolled from Aim 2's trial, we will explore perceived barriers to accessing, using, and applying mMT effectively. Purposive sampling informed by symptom trajectories and mMT app use pattern analytics will allow inclusion of responders and non-responders, as well as infrequent and frequent app users. Patients who participate in this Aim will be asked a series of questions to determine app access, use and content during a single study visit lasting 30-60 minutes.

Aim 4: Using lessons learned from Aims 2 & 3, operationalize the final optimized mMT system.

Consistent with NIH guidelines on mixed methods research¹ we will integrate quantitative (Aim 2) and qualitative (Aim 3) data from Years 2-4 to finalize the mMT app build that optimizes MOST outcomes of feasibility, usability, and clinical impact. After updating app software to current standards, we will ensure mMT reaches 'excellent' usability (mean SUS score ≥ 85) among a diverse purposive sample of up to 25 individuals—and is ready for off-the-shelf use in a next-step RCT.

4. Study Objectives, Hypotheses, and Outcomes

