If an individual states that they wish to drop out, the study team will respect that as well. A follow-up question may be asked to ascertain the reason for withdraw; however, this is for documentation purposes only. Additionally, the study and/or site PI retain the right with withdraw the participant from the study if they feel that participation is no longer in the participant's best interest and/or the participant is non-compliant despite numerous attempts to contact by the study team.

Vulnerable Populations

This project will not enroll individuals from vulnerable populations (e.g., imprisoned persons, minors).

Adverse events (AEs), serious adverse events, (SAEs) and unanticipated problems (UPs).

It is recognized that there is a slight risk that some participants may become distressed when completing self-report measures or participating in interviews. When necessary, participants who experience psychological distress *related to completing questionnaires* will be referred for appropriate psychiatric or psychological care. All participants will have access to the PI's contact information 24 hours a day (shown in the consent form). If a telephone interview is required, a trained study team member who has been trained to be sensitive to the nature of these issues will conduct it.

It is anticipated, in this study, for AEs to be extremely rare as it is a behavioral study. However, it is possible that participants could become distressed in a hospital setting or post-discharge due to increased illness and/or limitations. As such, participants could exhibit signs of and/or experience suicidal ideations or be admitted for mental health symptoms. Therefore, for this study, only increased levels of distress related to completing the questionnaires or completing the coping skills practice and/or suicidal ideations will be considered AEs.

Like, AEs, it is not anticipated that SAEs will occur. However, for this study, an SAE would be defined as a suicide attempt, a hospitalization (post hospitalization that initiated the patient's eligibility for study participation), or death. All serious adverse events will be reported within the standard timelines required to the IRB, study sponsor, and/or DSMB, as appropriate and when applicable.

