The initial DSMB meeting will occur before the initiation of subject enrollment for the purpose of updating members on the study, ensuring agreement on the review process, establishing the review methodology and procedures, ensuring all conflicts of interest are disclosed (to be reviewed by NHLBI staff), reviewing the protocol, and codifying a written charter. The NHLBI's Data Safety Monitoring Plan (DSMP) Template will be used to guide the drafting of the charter. This document will specify procedures for protocol amendments, ensuring participant confidentiality and privacy, ensuring database protection, coordinating center responsibilities, creating adverse outcome definitions (adverse events, unanticipated problems, and serious adverse events), protocol for reporting and responding to adverse events while also maintaining subject confidentiality, justifying sample size, assessing accrual and compliance, halting and stopping rules (drafted with the assistance of the DSMB chair and the DSMB lead statistician), approving informed consent documents, and guidelines for quality control and quality assurance. Before enrollment begins, the DSMB charter will be approved by both the DSMB and the NHLBI; additionally, ClinicalTrials.gov registration will be finalized as per the Milestone Plan shown in the Research Strategy document.

The first DSMB data review will occur either after the first 60 participants have been enrolled or enrollment has occurred for 6 months, whichever is observed first. Thereafter, the DSMB will review cleaned data reports (provided by the Project Manager 2 weeks before the DSMB meeting) every 3 months during enrollment and follow up, and will prepare a report with any recommendations within 2 weeks following their review. The specific study metrics that the DSMB will review at each meeting include enrollment rate, dropout rate, HADS scores, PTSS scores, and Adverse Events. The primary safety measures will be Adverse Events reports and HADS scores.

Other items reviewed by the DSMB at each meeting will include: (a) data quality, completeness, and timeliness; (b) performance of the individual sites; (c) adequacy of compliance with goals for recruitment and

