retention, including women and minorities; (d) protocol adherence; and (e) presence of factors that could adversely affect study outcome or compromise data confidentiality. Study participants will be recovering from life-threatening illnesses managed in intensive care units, which increase the likelihood of death overtime in comparison to healthy individuals. As such, any patient deaths and their cause during the follow up period will be recorded, discussed, and highly scrutinized.

The study biostatistician will oversee any DSMB statistical requests and interpretations. During the review process, formal statistical tests may be performed under DSMB supervision if requested (e.g., examining the differences in Adverse Event or outcome rates between factor-based groups). Additionally, the DSMB may request a formal statistical assessment if a suspicious increase in HADS score is observed in any factor-based group. If a specific factor group is found to have a statistically significant increase in HADS score, the DSMB scope of action may include recommendation for stopping the trial. For differences in study dropout rates, appropriate changes to the protocol will be made by PI consensus after DSMB member input. Any protocol changes, as well as any adverse events, will also be immediately reported to the relevant site IRB, the Central Institutional Review Board (located at Duke University), as well as to the NHLBI Program Officer.

Quality Assurance and Confidentiality

First, the electronic data entry system “forces” responses to key questionnaire items (e.g., primary outcomes surveys) before allowing progression through the particular interview’s template, thereby minimizing missing data. For less critical items, delayed data entry is possible (though these data elements are non-essential to primary aims analyses). However, each time the study team logs into the secure data entry system, prompts appear on the welcome screen that show what data elements remain incomplete (as well as the time frame within which they must be entered) for all site participants.

The study PI will ensure the validity of the data system by examining electronic summary case report forms within the EDC system to ensure adequacy and accuracy of data collection as well as transcription to the database itself after enrollment of the first 5 participants. Agreement will be reviewed and discrepancies will be discussed.

Confidentiality

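### Recorded adverse events may differ between factor levels through detection alone, because staff contact is both a way of finding events and part of what is randomised

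*Protocol*

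**What the plan says.** **The comparison.** Protocol Section 14 (DSMB) states that "formal statistical tests may be performed under DSMB supervision if requested", and gives as an example "examining the differences in Adverse Event or outcome rates between factor-based groups". The same section says "The primary safety measures will be Adverse Events reports" together with HADS scores. HADS is in none of the survey lists in Protocol Sections 3, 4 and 7, so adverse event reports are the only primary safety measure with a described data source.

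**What counts as an event.** The Abbreviations and Definitions say "an AE will be considered any suicidal ideation", and nothing else. Section 12 is wider: "only increased levels of distress related to completing the questionnaires or completing the coping skills practice and/or suicidal ideations will be considered AEs".

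**How events are found.** The Suicidality Response Plan in Section 12 names two routes. The first is that "delegated study team members may have in-person or telephone interactions that concern them". The second is an app alert built on PHQ-9 item 9 followed by an intent item. Section 12 adds an inquiry about events at each study visit, by request to the participant and/or record review.

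**What sets staff contact.** Section 3 (Aim 2) randomises initiation (therapist call or app) and the stepped response to symptoms (therapist or app). Depending on the group, patients may have a therapist introduction and then "receive frequent follow-ups from the study therapist to provide training, education and support". The high-dose level adds an anonymous support function that a study interventionist proctors.

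**What is not said.** Neither document says how a comparison of event rates would deal with unequal contact. The SAP has no adverse event analysis. The DSMB charter, to which Section 14 assigns event definitions and the reporting protocol, is not among the documents.

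**The concern.** A count of recorded events reflects both how often events happen and how likely each one is to be noticed. If the second part depends on the randomised factor, the comparison of counts is not a comparison of harm.

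Two errors are possible. A therapist level could look less safe only because someone was listening. Harm at an app level could also go under-recorded. The second matters here because Section 4 expects the best package to be app-initiated and app-based, and SAP Table 3 makes the app the default level for both components. Under-detection would flatter the levels already favoured.

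The DSMB sees adverse events at every meeting, tested or not, and may recommend changing or stopping the trial.

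**Working it through.** **1. The plan's own figures.** The documents give no event rate, detection rate or power for a safety comparison. The only sizing figure is for PHQ-9. With the SAP Appendix B covariances, the T2 standard deviation given baseline is √(19.28 − 9.67²/27.95) = 3.99. With 96 per factor level, power for 1.6 units is 79.3%, against 79.8% in SAP Table 2. That figure reproduces and is not in dispute.

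**2. Detection routes side by side.**

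| Route | Where | Same in all groups? |
|---|---|---|
| App surveys at T1, T2, T3 | Protocol Appendix 1 | Yes |
| App alert (item 9, then intent) | Section 12 | Yes |
| Weekly check-in | Section 7, Appendix 1 | Yes |
| Inquiry and/or record review at visits | Section 12, Appendix 1 | Yes |
| Telephone contact with most participants | Section 12, Reporting Procedures | Not tied to a factor |
| Therapist introduction and follow-up | Section 3 | No, set by two factors |
| Proctored support function | Section 3 | No, high dose only |

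**3. Gaps in the common routes.**
- The alert table in Section 12 lists no action by app or team when item 9 is non-zero and intent is denied, yet the Definitions count any ideation as an event. Other sentences in Section 12 say the response plan could be activated, and a call made, for ideation as such. The text does not settle whether ideation without intent becomes an event record through the app.
- No app item is described that attributes distress to questionnaires or skills practice, which Section 12 also counts.
- Scheduled inquiry may be record review alone. Appendix 1 places it at baseline, T1, T2 and T3, with none between T1 and T2, the active month.
- The content of the weekly check-ins is not given in enough detail to say that they include item 9.

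**4. Size under assumptions.** Let p be the true risk (equal at both levels), s the share of events found by common routes, and t the share of the remainder found by extra therapist contact. None of the three is in the documents. The observed rate is p·s at the app level and p·(s + (1 − s)·t) at the therapist level, so the rate ratio is (s + (1 − s)·t)/s. For example, s = 0.6 gives (0.6 + 0.4 × 0.5)/0.6 = 1.33 with t = 0.5, and (0.6 + 0.4 × 0.25)/0.6 = 1.17 with t = 0.25.

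SAP Section 2.4 has 30 per condition, so each factor compares 4 × 30 = 120 with 120. The last two columns give the exact binomial probability that a pooled z test at two-sided 0.05 shows a significant excess at the therapist level.

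| s | t | Rate ratio | Expected events at p = 5% (app, therapist) | False excess, p = 5% | False excess, p = 20% |
|---|---|---|---|---|---|
| 1.0 | 0 | 1.00 | 6.0, 6.0 | 2.4% | 2.6% |
| 0.9 | 0.5 | 1.06 | 5.4, 5.7 | 2.8% | 4.0% |
| 0.7 | 0.5 | 1.21 | 4.2, 5.1 | 4.2% | 9.5% |
| 0.5 | 0.5 | 1.50 | 3.0, 4.5 | 6.8% | 21.4% |
| 0.5 | 1.0 | 2.00 | 3.0, 6.0 | 15.4% | 59.3% |

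With Fisher's exact test at p = 5%, the four biased rows give 1.3%, 2.0%, 3.0% and 8.7%, against 1.1% with no bias.

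**5. What would cancel it.** A true reduction in risk from therapist contact of 1 − s/(s + (1 − s)·t) offsets the artefact: 5%, 18%, 33% and 50% for the four biased rows in order.

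**The case against.** The strongest reply is that detection is largely common to all groups. Every randomised participant has the app surveys, the alert, a weekly check-in and the visit inquiry. Section 7 has staff contact anyone with an alert, or a distress score above T1, at T2 and T3. Section 12 promises telephone contact with most participants, whatever their group. The factor-set contact may also be modest: initiation is by a call, and the stepped response follows symptoms already registered. This stands, and it is why the effect can only be called possible.

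A reader might infer that therapist levels will look more harmful. The documents do not support that: the share of events that only extra contact would reveal is unknown, and therapist contact might lower true risk.

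A reader might also infer that a difference in event counts would stop the trial or decide a component. Section 14 links stopping to a significant HADS increase, not to an event count. Component selection in SAP Sections 1.1 and 4 rests on PHQ-9, then secondary outcomes, feasibility and acceptability; adverse events are not named. The tests are optional, and Section 12 expects few events, so at 5% risk most scenarios rarely give a significant false signal.

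Finally, the unseen charter may already deal with this, so it cannot be said to be unhandled. What remains is that few events make false significance less likely but do not make the counts comparable, and neither supplied document contains a safeguard.

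**Conclusion.** The concern holds as a possibility of unequal ascertainment, not as a predicted result. The protocol permits event rates to be compared between factor groups, some events are found through staff contact, and randomisation sets part of that contact. Therapist levels may show more recorded events, or app levels fewer, through detection alone. The high-dose channel raises the same issue to a lesser degree, since it is anonymous.

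The direction is plausible but the size is unknown. It is near nil if common routes find most events (rate ratio 1.06 with s = 0.9, t = 0.5) and material if they find half (1.50 to 2.00). These figures rest wholly on assumed p, s and t. The 20% risk column is hard to square with the protocol's expectation that events will be very uncommon, so the 5% column is the more relevant. SAEs sought by record review are less exposed.

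This does not touch the primary PHQ-9 analysis. It is a cheap improvement to safety reporting that should be made.

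**What to change.** In Protocol Section 14:

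- Make the main between-factor safety comparison one of measures collected identically in all groups: PHQ-9 item 9 with the intent item at T2 and T3, PHQ-9 worsening from T1, and SAEs from the scheduled inquiry and record review.
- Add a detection-route field to the adverse event form (app, scheduled inquiry or record review, staff contact, support function). For events already recorded, the contact log described in Section 12 may show the route.
- Show all adverse event counts by factor level, split by route, for all three factors. Report contact-detected events to the DSMB in full, labelled as subject to unequal ascertainment. They should not be barred from review, because distress related to skills practice may surface only through contact.
- Reconcile the adverse event definitions in the Abbreviations and in Section 12 before any rate is compared. Check the charter for consistency with both.

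The cost is one form field and some report wording; every event is still reported. The main drawback is that survey measures are missing for participants who drop out (Section 9 assumes 20% by T2), and contact could affect completion. Completion by factor level should therefore be shown beside the comparison.
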